Trial Protocol Version 12 Proprietary confidential information. © 2022 Boehringer Ingelheim International GmbH or one or more of its affiliated companies. All rights reserved.

Second Primary Malignancies

Cases of second primary malignancies have been reported in patients treated with enzalutamide in clinical studies. In phase 3 clinical studies, the most frequently reported events in enzalutamide treated patients, and greater than placebo, were bladder cancer (0.3%), adenocarcinoma of the colon (0.2%), transitional cell carcinoma (0.2%) and bladder transitional cell carcinoma (0.1%). Patients should be advised to promptly seek the attention of their physician if they notice signs of gastrointestinal bleeding, macroscopic haematuria, or other symptoms such as dysuria or urinary urgency develop during treatment with enzalutamide.

Hypersensitivity reactions

Hypersensitivity reactions manifested by symptoms including, but not limited to, rash, or face, tongue, lip, or pharyngeal oedema, have been observed with enzalutamide. Severe cutaneous adverse reactions (SCARs) have been reported with enzalutamide. At the time of prescription patients should be advised of the signs and symptoms and monitored closely for skin reactions.

Proprietary confidential information. © 2022 Boehringer Ingelheim International GmbH or one or more of its affiliated companies. All rights reserved.

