3.3.5 Replacement of patients

For phase Ib escalation:

Patients will be replaced for determination of the primary endpoint (MTD) in cases of:

- Patient's withdrawal during the first cycle of treatment for reasons other than DLT, e.g. patient no longer wishes to participate, or lost to follow up during first cycle.
- Patients who do not experience DLT, but miss more than one dose of BI 836845 during the first cycle of treatment.
- Patients who do not experience DLT, but miss 3 or more consecutive doses of enzalutamide during the first cycle of treatment.
- Patients who miss one complete cycle at any time beyond the first cycle of treatment may be replaced after discussion between the sponsor and the investigator.
- Patients who are non-evaluable with respect to DLT.
- Patients with CTCAE grade ≥3 allergic reaction/hypersensitivity to the study drug(s) within the first cycle will be replaced.

Patients that have been replaced might continue treatment in the trial should criteria in section 4.1.4.4 apply; however these patients will not be considered for analysis of the primary endpoint of this part.

For phase Ib expansion cohort:

Patients who withdraw after assignment but before start of therapy will be replaced.

BI Trial No.: 1280.8 Doc. No.: c02304008-15

Trial Protocol Version 12 Proprietary confidential information. © 2022 Boehringer Ingelheim International GmbH or one or more of its affiliated companies. All rights reserved.

4. **TREATMENTS**

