CTCAE Grade 4	Patients experiencing CTCAE grade 4 such as anaphylaxis during an infusion should have infusion immediately stopped and receive appropriate treatment including use of resuscitation medications and equipment that must be available. Such patients should NOT receive any further BI 836845 treatment.

BI Trial No.: 1280.8 Doc. No.: c02304008-15 Trial Protocol Version 12

Proprietary confidential information. © 2022 Boehringer Ingelheim International GmbH or one or more of its affiliated companies. All rights reserved.

Page 56 of 241

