5.2.3 Dose Limiting Toxicity (DLT) definitions

DLTs will be assessed during the phase Ib escalation part of the study. The determination of the number of DLTs experienced during the first cycle of treatment will be used to identify the MTD of BI 836845 in combination with enzalutamide.

A study drug-related adverse event constitutes a DLT, if one of the following applies during treatment in the phase Ib escalation cohort:

- AST or ALT > 5x ULN (for baseline AST/ALT \leq ULN) or > (baseline value + 4x ULN) (for baseline AST/ALT > ULN)
- CTCAE Grade 3 or 4 toxicity (except for incompletely treated nausea, untreated vomiting, untreated diarrhoea, fatigue, infusion reaction, electrolyte, or AST/ALT).
- CTCAE Grade ≥2 infusion reaction despite adequate pre-medication.
- CTCAE Grade ≥2 nausea and/or vomiting persisting for 7 or more days despite antiemetic treatment.
- Any grade 4 hyperglycaemia (symptomatic or asymptomatic).
- Any Grade 3 hyperglycaemia lasting >48 hours.
- Any electrolyte grade 3 AE which is refractory to optimal correction therapy
- Seizure event of any CTCAE grade
- No recovery from a non-DLT CTCAE grade >2 toxicity to grade 1 within 14 days of administered dose
- Sustained fatigue/asthenia grade 3 for longer than 96 hours associated with deterioration of ECOG Performance Score
- Any other study drug related toxicity at any time point during the study considered significant enough to be qualified as DLT in the opinion of the investigators and confirmed by the safety review with the BI clinical monitor, will be reported as a DLT.

It is essential that patients are treated sufficiently according to supportive care standards.

As patients with a documented clinical benefit, e.g. objective tumour response or absence of tumour progression, will receive further treatment with the trial drug all DLT events in individual patients occurring at any time during treatment cycles, or the follow-up period, must be reported as an AESI.

BI Trial No.: 1280.8 Doc. No.: c02304008-15

Trial Protocol Version 12 Page 70 of 241

Proprietary confidential information. © 2022 Boehringer Ingelheim International GmbH or one or more of its affiliated companies. All rights reserved.

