10.5 COMMON TERMINOLGY CRITERIA FOR ADVERSE EVENTS (CTCAE)

The CTCAE version 4.03, 14 June 2010(R10-4848) will be use to classify and record the intensity of adverse events in the (e)CRF.

Grading of Hypersensitivity Reactions According to the National Cancer Institute CTCAE version 4.03, 14 June 2010, described above, will be used for the grading of infusion reactions and subsequent management will be according to the protocol and/or local hospital guidelines.

Trial Protocol Version 12

Page 120 of 241

Page 122 of 241

Boehringer Ingelheim BI Trial No.: 1280.8 Doc. No.: c02304008-15

Boehringer Ingelheim
06 Jun 2022

Trial Protocol Version 12

Page 123 of 241

Page 124 of 241

Trial Protocol Version 12

Page 125 of 241

Trial Protocol Version 12

Page 130 of 241

Trial Protocol Version 12

Page 134 of 241

Doc. No.: c02304008-15 **Trial Protocol Version 12** Page 135 of 241 Proprietary confidential information. © 2022 Boehringer Ingelheim International GmbH or one or more of its affiliated companies. All rights reserved.

Trial Protocol Version 12

Page 136 of 241

[figure not shown]

Page 139 of 241

10.7 EXAMPLES OF BONE SCAN PROGRESSIONS USING PROSTATE CANCER CLINICAL TRIALS WORKING GROUP GUIDELINES (PCWG2)

BL = Baseline

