Hepatic impairment	search SMQ		
Uvnaralyanamia narrayy	SMQ: Hyperglycaemia/new onset diabetes mellitus		
Hyperglycaemia narrow Narrow			
	BIcMQ:		
Infusion related reaction	PT list of Infusion related reaction		
infusion related reaction	AND		
	SMQ Hypersensitivity Narrow		
Non-infectious pneumonitis	SMQ: Interstitial lung disease Narrow		
Renal insufficiency	SMQ: Acute renal failure Broad		
Weight loss	BIcMQ:		
Weight loss	Weight loss - Broad		
Neutropenia	SMQ: Haematopoietic leukopenia – Narrow		
Stomatitis	BIcMQ:		
Stomatitis PT list			
Asthenia	BIcMQ:		
Asincilla	Asthenic conditions – Narrow		
Anemia	SMQ: Haematopoietic erythropenia		
Thrombocytopenia	SMQ: Haematopoietic thrombocytopenia		

This column indicates whether the Term(s) provided in the first column are MedDRA preferred terms (PT), Standardised MedDRA Queries (SMQ) or BI customised MedDRA Queries (BIcMQ).

The incidence of AE by UDAEC will be analysed.

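### A narrow set of cycle 1 grade ≥3 allergic reactions is both a DLT (Protocol 5.2.3) and a trigger for replacement (3.3.5), and nothing settles whether it counts towards the MTD

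*Protocol*

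**What the plan says.** **What is a DLT.** Protocol 5.2.3 makes a study-drug-related grade 3 or 4 toxicity a DLT, apart from a bracketed list of exceptions. The list ends with "untreated diarrhoea, fatigue, infusion reaction, electrolyte, or AST/ALT". It names infusion reaction but not allergic reaction or hypersensitivity. A separate criterion brings some infusion reactions back in: "CTCAE Grade ≥2 infusion reaction despite adequate pre-medication".

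**Who is replaced.** Protocol 3.3.5 lists the escalation patients to be replaced for the MTD. One bullet reads "Patients with CTCAE grade ≥3 allergic reaction/hypersensitivity to the study drug(s) within the first cycle will be replaced". The withdrawal bullet and both missed-dose bullets apply only where there is no DLT, for example "Patients who do not experience DLT, but miss more than one dose of BI 836845 during the first cycle of treatment". The hypersensitivity bullet has no such condition.

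**What replacement does.** Section 3.3.5 removes replaced patients from the primary endpoint of that part. SAP 6.3 (MTD set), 7.4.1 and 7.8 repeat that they are excluded from the MTD determination.

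**What pulls the other way.** Protocol 5.2.4 defines the MTD by at most 1 of 6 patients with a drug-related DLT in cycle 1 and makes no exception for allergic events. Protocol 4.1.4.1 replaces patients who do not complete cycle 1 only if the reason is not a DLT, and refers back to 3.3.5. SAP 7.4.1 decides replacement case by case, with the exclusions confirmed by the trial team before database lock.

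**The concern.** A severe allergic reaction in cycle 1 can satisfy 5.2.3 and 3.3.5 at once. Under 5.2.3 and 5.2.4 it is one of the events that decide whether a dose is tolerable. Under 3.3.5 and the SAP the patient leaves the count and another takes the place. The MTD is a primary endpoint of the escalation part and turns on one patient in six, so moving one patient can change the formal result. Whoever assembles the MTD set has texts that give opposite answers, and a case-by-case step with no criterion for choosing between them.

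**Working it through.** **1. Which events fall under both rules.**

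| Cycle 1 event, grade ≥3, drug-related | DLT under 5.2.3? | Replaced under 3.3.5? |
|---|---|---|
| Allergic reaction that is not an infusion reaction, grade 3/4 | Yes, grade 3/4 criterion; hypersensitivity is not excepted | Yes |
| Allergic infusion reaction despite adequate pre-medication | Yes, infusion-reaction criterion | Yes |
| Allergic infusion reaction without pre-medication | Not by either of these two criteria | Yes |

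Only the first two rows conflict. An example of the first is a reaction to the oral drug: Protocol 1.2.2 says "Hypersensitivity reactions manifested by symptoms including, but not limited to, rash, or face, tongue, lip, or pharyngeal oedema, have been observed with enzalutamide" (text added in 2022, no rate given).

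The overlap is narrow because the documents mostly treat hypersensitivity to the antibody as an infusion reaction. Protocol 10.5 says that the hypersensitivity grading "described above, will be used for the grading of infusion reactions". The grade 4 row of Table 4.2.1.1:1 covers "Patients experiencing CTCAE grade 4 such as anaphylaxis during an infusion". SAP Table 7.8.1:1 puts "SMQ Hypersensitivity Narrow" under infusion-related reaction.

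**2. The plan's own figure.** Section 5.2.4 equates 1 of 6 with an incidence of no more than 17%: 1/6 = 0.167. This reproduces.

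**3. What one replacement can do.** Seven patients are treated. One has an allergic DLT and is replaced; one of the other six has a different DLT. The formal count is 1/6 = 16.7%, which passes. Among treated patients it is 2/7 = 28.6%.

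**4. Size under assumed rates.** Let r be the risk per patient of an event in the overlap and o the risk of any other cycle 1 DLT, taken as independent. Both are assumptions.

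- r = 1% is illustrative. r = 3.6% is the one-sided 95% upper bound from 0 infusion reactions in 81 monotherapy patients (Protocol 1.2.1): 1 − 0.05^(1/81) = 0.0363. That bound covers infusion reactions of any grade, so it is a high-end value for the antibody. It does not cover enzalutamide.
- o = 1/81 uses the one DLT reported separately in Protocol 1.2.1. o = 10% is illustrative and has no source in the documents.

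If the event is counted, the risk per patient is p = 1 − (1 − o)(1 − r). If the patient is replaced, it is p = o. The chance of passing is P = (1 − p)^6 + 6p(1 − p)^5. For example, o = 0.10 and r = 0.01 give p = 1 − 0.90 × 0.99 = 0.109 and P = 0.868, against 0.886 at p = 0.10.

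The chance that a dose passes under replacement although at least 2 treated patients had a cycle 1 DLT is P(X=0)[1 − P(K=0) − P(K=1)] + P(X=1)[1 − P(K=0)]. Here X is binomial(6, o) and K is the number replaced before six remain, with P(K=0) = (1 − r)^6 and P(K=1) = 6r(1 − r)^6. For o = 0.10 and r = 0.01 this is 0.5314 × 0.0020 + 0.3543 × 0.0585 = 0.022.

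| o | r | Pass if counted | Pass if replaced | Difference | Passes with ≥2 treated patients having a DLT |
|---|---|---|---|---|---|
| 10% | 1% | 0.868 | 0.886 | 0.018 | 0.022 |
| 10% | 3.6% | 0.816 | 0.886 | 0.069 | 0.084 |
| 1/81 | 1% | 0.993 | 0.998 | 0.005 | 0.006 |
| 1/81 | 3.6% | 0.969 | 0.998 | 0.028 | 0.037 |

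**The case against.** **It may be deliberate.** The hypersensitivity bullet is the specific rule on its subject, and severe allergy is often set aside because it says little about dose. Enzalutamide is fixed at 160 mg at both dose levels, so an allergic reaction to it bears little on whether 750 mg or 1000 mg of the antibody is tolerable. This is a fair reading of intent, but 5.2.3 does not carry it out: it excepts infusion reactions from the grade 3/4 criterion and leaves hypersensitivity in. The texts still conflict.

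**Other provisions protect the count.** Sections 5.2.4 and 4.1.4.1 and the case-by-case review in SAP 7.4.1 all allow a patient with a DLT to be kept. This stands against a stronger reading that a reader might infer, namely that the plan systematically strips allergic DLTs out of the MTD. The documents do not support that. They contain competing provisions, and the trial team could have kept such a patient. But none of them settles the matter: 5.2.4 does not mention replacement, 4.1.4.1 covers only an incomplete first cycle, and SAP 7.4.1 gives no criterion.

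**The dose decision is protected.** DLTs in escalation are adverse events of special interest (5.2.2.1) and are tabulated by dose cohort (7.3.3). Escalation decisions consider all available toxicity data (5.2.3), and the phase II dose rests on the totality of safety data (5.2.4). The plot in SAP 7.4.1 shows replaced patients and patients with DLTs. This stands in full. It confines the problem to the formal MTD count.

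**Conclusion.** The conflict is real and minor. It covers the two event types in step 1 and no others. Reading every cycle 1 grade ≥3 allergic reaction as a DLT lost from the count would go too far, because an allergic infusion reaction without pre-medication meets neither of the two DLT criteria.

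Following 3.3.5 to the letter could let a cohort with 2 DLTs in 7 treated patients be recorded as 1/6. The pass probabilities rest on assumed rates and on independence. With the document-based 1/81 for other DLTs and an assumed 1% for the overlap, the change is 0.005; the largest value, 0.069, needs the high-end 3.6% and an unsourced 10%.

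A reader might also infer that the MTD was misreported or that the phase II dose is unsafe. The documents support neither. They show no affected patient, and the decision-makers would have seen the event. The SAP Introduction says that the escalation safety analyses have already been documented in an interim report, so what remains is whether the reported count is right.

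**What to change.** - **Protocol 3.3.5:** open the hypersensitivity bullet with the same non-DLT condition that the missed-dose bullets carry. It then still covers its natural case, an allergic infusion reaction without pre-medication.
- **SAP 6.3, 7.4.1 and 7.8:** state that a patient with an event meeting 5.2.3 in the MTD evaluation period stays in the MTD set.
- **Now:** as escalation is already reported, check the replaced escalation patients against 5.2.3. If any met it, report the count against the 1-of-6 limit with and without them, labelled post hoc. If none did, one sentence saying so closes the point.

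The cost is one protocol clause, one sentence in each of three SAP sections, and a check of any replaced patients in a part planned for about 9 to 12. The text change no longer alters how any escalation patient is handled. The downside is a recount made after the dose was chosen, which may be less favourable than the one reported.

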4.1 TREATMENTS TO BE ADMINISTERED

4.1.1 Identity of BI investigational product and comparator product(s)

Substance: BI 836845 humanised monoclonal antibody

Pharmaceutical form: Liquid formulation

Source: Boehringer Ingelheim Pharma GmbH & Co. KG

Unit strength: 10 mg/ml of BI 836845 supplied in 20 ml vials. Appropriate dose

of BI 836845 will be diluted in physiological sodium chloride

solution (0.9%).

Duration of use: One hour at the start of each week (Day 1, 8, 15 and 22) of a 28

> day cycle of treatment until disease progression or undue toxicities. Infusion duration may be extended to over one hour in case of

Page 45 of 241

infusion reaction or adverse events.

Route of administration: Intravenous

Starting dose: 750 mg (possible dose adjustments to 500 mg and 1000 mg) total

dose by one hour i.v. infusion

Additional information: Starting dose may be adjusted during phase Ib tolerability/safety

and dose finding phase

Substance: Enzalutamide (Xtandi®)

Pharmaceutical form: Liquid-filled soft gelatin capsule or film-coated tablets

Source:

Unit strength: 40 mg or 80mg

Daily dose during each 28 day cycle of treatment Duration of use:

Route of administration: Oral

160 mg (possible dose adjustments to 120 mg and 80 mg) daily as Starting dose:

per SPC

Additional information: None

Page 46 of 241

BI Trial No.: 1280.8 Doc. No.: c02304008-15

Proprietary confidential information. © 2022 Boehringer Ingelheim International GmbH or one or more of its affiliated companies. All rights reserved.

4.1.2 Method of assigning patients to treatment groups

Patients meeting the inclusion criteria and none of the exclusion criteria and who have given written informed consent are eligible for participation in the study.

Patients entering Phase Ib:

- At least 9-12 eligible patients will be entered into the safety and tolerability phase Ib, dose escalation part of the study and receive BI 836845 plus enzalutamide. Patients will be entered in a 3+3 design with a single dose escalation, dependent on DLTs observed.
- Approximately 25 patients will be entered into the exploratory expansion cohort at the MTD and/or recommended phase II dose (RP2D) determined from the above safety and tolerability phase.

Patients entering Phase II will be randomised at the first visit of Cycle 1 in a 1:1 ratio to either:

- Arm A and receive BI 836845 plus enzalutamide, or
- Arm B and receive enzalutamide alone

Treatment assignment in the randomised trial will be by means of a third-party phone /web-based randomisation during the screening phase. This will involve the use of an interactive response technology (IRT i.e. Interactive Voice Response System [IVRS]/Interactive Web Response System [IWRS]). To facilitate the use of the IRT, the investigator will receive an IRT worksheet for each patient with the complete IRT dialogue and all necessary instructions for using the IRT.

4.1.3 Selection of doses in the trial

4.1.3.1 BI 836845

The dose level and frequency of BI 836845 was determined following phase I dose escalation studies in both a weekly (U11-3025) and 3-weekly dosing scheme (U10-2994). Minimal protocol defined DLTs were observed and no MTD was reached in either study; however a relevant biological dose was determined.

A dose of BI 836845 is considered biologically relevant, when concentrations of free IGF-1 and free IGF-2 are considerably reduced over time. Free IGF-1 and free IGF-2 plasma concentrations are not measured in studies 1280.1 and 1280.2. Therefore a semi-mechanistic PK/PD model was developed describing the time-dependent kinetics of and the interaction between BI 836845 and the different PD biomarkers (i.e. IGF-1, IGF-2, and IGFBP3) over time. Simulations using this model indicate that a weekly dosing of 1000 mg BI 836845 reduces free IGF-1 concentration by more than 90% and in addition free IGF-2 by 64 % at trough steady-state relative to pre-treatment; this is considered a relevant biological effect. Therefore, a weekly dose of 1000 mg BI 836845 is considered a suitable dose.

Page 47 of 241

Proprietary confidential information. © 2022 Boehringer Ingelheim International GmbH or one or more of its affiliated companies. All rights reserved.

The exact dose of BI 836845 to be used in the expansion cohort and combination treatment arm of the phase II study will be determined during the phase Ib tolerability and safety phase, (phase Ib escalation phase) see section 4.1.3.3.

4.1.3.2 Enzalutamide

The recommended dose of enzalutamide, as per the SPC, is 160 mg (four 40 mg capsules, four 40mg tablets or two 80mg tablets) administered orally once daily and can be taken with or without food (for dosing instructions on PK sampling visits see below).

4.1.3.3 Determination of the dose of BI 836845 in combination with enzalutamide

The phase Ib tolerability and safety phase (phase Ib escalation cohort) will be performed to determine the MTD, recommended phase II dose (RP2D) of BI 836845 in combination with enzalutamide using a 3+3 design in order to confirm the recommended dose to be used in the phase II randomised trial and exploratory expansion cohort.

Dosing with BI 836845 will be as follows:

- The starting dose of BI 836845 will be 750 mg (75%) total dose plus 160 mg (100%) daily dose of enzalutamide.
 - If 0 out of 3 patients experience a DLT enter 3 patients at highest dose of BI 836845
 - If 1 out of 3 patients experience a DLT enter 3 more patients at starting dose of BI 836845.
 - If 0 of 3 of these additional patients experience a DLT move to highest dose of BI 836845.
 - If ≥ 1 out of 3 of these additional patients experience a DLT trial is stopped.
 - o If ≥ 2 out of 3 patients experience a DLT trial is stopped.
- The highest dose of BI 836845 will be 1000 mg (100%) total dose plus 160 mg (100%) daily dose of enzalutamide.
 - o If \leq 1 out of 3 patients experience a DLT enter 3 additional patients at highest dose of BI 836845.
 - o If \geq 2 out of 3 patients experience a DLT:
 - If only 3 patients are entered at starting dose of BI 836845 enter additional 3 patients at starting dose of BI 836845
 - If 6 patients are already recruited in starting dose regimen recruitment into escalation part of trial is complete.

06 Jun 2022 **BI Trial No.: 1280.8**

Page 48 of 241

Trial Protocol Version 12 Proprietary confidential information. © 2022 Boehringer Ingelheim International GmbH or one or more of its affiliated companies. All rights reserved.

The MTD will be defined as the dose level at which one or less DLT is observed in six patients during the first cycle of treatment of each patient (28 days). See section 5.2.4

Non-evaluable patients for DLT will be replaced.

The decision on dose escalation and determination of next dose, the MTD, and/or recommended phase II dose (the exploratory expansion cohort will also use the same dose as Phase II) will be determined after discussion with the trial team comprising of at least one BI Clinical Monitor, BI project physician (TMM) and Coordinating Investigator, or designee, and taking into account patient safety.

